3.4.3.5. Abbreviated World Health Organization Quality of Life - Bref

Definition: the four domain scores (Physical, Psychological, Social Relations and Environment) will be calculated.

The WHOQOL-Bref questionnaire has been validated in parents of children with autistic disorder (Latefa *et al.*, 2014). The psychometric properties will be checked separately.

Analysis: A General Linear Model with the fixed categorical effect of treatment, country and gender as well as the continuous, fixed covariate of baseline will be used for the change from baseline to W026 in the four domains scores in the RS.

GENERAL LINEAR MODEL (ANCOVA): change = baseline country gender treatment

Missing data handling: missing data will be imputed using the multiple imputation approach (MI).

Statistical elements: the following elements will be provided in a summary table:

- Estimate (standard error) of the difference between adjusted treatment group means.
- Two-sided 95% CI of the estimate.

Supplementary analysis:

The four domains scores will be summarized using descriptive statistics and graphs:

- During the double-blind period: baseline, each planned post-baseline visit (W004, W008, W012 and W026) as well as change from baseline to each planned post-baseline visit will be described in the RS by treatment groups (S95008 vs placebo).
- During the open-label period: OL baseline, each OL planned post-baseline visit (W030, W034, W038 and W052) as well as change from OL planned baseline to each OL post-baseline visit will be described in the RSO for the Placebo/S95008 arm.
- During the combined period: baseline, each planned post-baseline visit as well as change from baseline to each planned post-baseline visit will be described in the RSC for the S95008/S95008 arm.

3.4.4. Subgroups analysis

Not applicable.

3.5. Exploratory analysis**3.5.1. EuroQoL – 5-Dimension – Three-level**

Definition: The EuroQoL-5D-3L questionnaire (EQ-5D) is composed of 5 dimensions (mobility, self-care, usual activities, pain/discomfort and anxiety/depression), and a Visual Analog Scale (EQ-5D VAS).

The dimensional 5-level system will be converted into a single index utility score (EQ-5D index score).

Psychometric properties of the EQ-5D-3L Questionnaire were studying in caregivers of autistic children (Khanna *et al.*, 2013).

The psychometric properties will be checked separately.

Analysis:

A General Linear Model with the fixed categorical effect of treatment, country and gender as well as the continuous, fixed covariate of baseline will be used for the change from baseline to W026 in the EQ-5D index score (resp. EQ-5D VAS) in the RS.

GENERAL LINEAR MODEL: change = baseline country gender treatment

Missing data handling: missing data will be imputed using the multiple imputation approach (MI).

Statistical elements: the following elements will be provided in a summary table:

- Estimate (standard error) of the difference between adjusted treatment group means.
- Two-sided 95% CI of the estimate.

Supplementary analysis:

The EQ-5D VAS and the EQ-5D index score will be summarized using descriptive statistics and graphs:

- During the double-blind period: baseline and change from baseline to each post-baseline visit will be described in the RS by treatment groups (S95008 vs placebo).
- During the open-label period: OL baseline and change from OL baseline to each OL post-baseline visit will be described in the RSO for the Placebo/S95008 arm for patients.
- During the combined period: baseline and change from baseline to each post-baseline visit will be described in the RSC for the S95008/S95008 arm.

3.6. Safety analysis

All safety analyses will be performed on the taken treatment at W000 as following:

- For the double-blind period in the SS by treatment group (S95008 vs placebo).
- For the open-label period: in the SSO on the Placebo/S95008 arm.
- For the combined period: in the SSC on the S95008/S95008 arm.

Six periods are of interest to present accurately the safety endpoints. The start and end date of these periods are summarized in the following table:

Table (3.6) 1 - Definition of periods of emergence for safety events

| Period ID | ANALYSIS PERIOD | START | END |
|------------------|--|--|--|
| #1 | Emergent during the double-blind period | First intake in double-blind | End of double-blind period (including W26) |
| #2 | Treatment Emergent during the double-blind period | First intake in double-blind | Min(Last intake in double-blind + 2 days, First intake in open-label) |
| #3 | Emergent during the open-label period | First intake in open-label (W26 not included) | End of open-label period (including W52 and follow-up) |
| #4 | Treatment Emergent during the open-label period | First intake in open-label (W26 not included) | Last intake in open-label + 2 days (included) |
| #5 | Emergent from the combined period | First intake in double-blind | End of open-label period (including W52 and follow-up) |
| #6 | Treatment Emergent from the combined period | First intake in double-blind | Last intake in open-label + 2 days (included) |

Listing of main safety data (including adverse events) and start/end date of each period will be provided for:

- Patients who had a delay superior to 30 days between the double-blind and the open-label period will be listed separately.

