Following the completion of the phase II, a Committee for Medicinal Products for Human Use (CHMP) Scientific Advice procedure was performed beginning 2017 to discuss the bumetanide phase III development plan in ASD paediatric patients. A randomised, placebo controlled study design with a 6-month double-blind treatment period followed by a 6-month open labelled extension period was considered by the CHMP as the most appropriate to have a comprehensive bumetanide efficacy and safety assessment. A modification to the agreed PIP has been submitted to the Paediatric Committee (PDCO) of the European Medicine Agency (EMA) and has received a positive decision (European Medicines Agency decision EMA-001303-PIP01-12-M02 dated 10th November 2017).

The present study (CL3-95008-002) will be performed in children from 2 to less than 7 years old presenting with ASD. A 6-month double-blind treatment period will be performed in which efficacy and safety of bumetanide 0.5mg BID will be assessed *versus* placebo. This double-blind period will be followed by a 6-month open label treatment period of bumetanide 0.5mg BID in which long term safety will be evaluated and a 6 weeks discontinuation phase. Bumetanide dose will be adapted on body-weight.

The present phase III bumetanide paediatric study has been developed based on the European Guideline and validated by the Paediatric Committee in the European Medicinal Agency (European Medicines Agency decision, EMA-001303-PIP01-12-M02 dated 10th November 2017). In this development program all children (even the placebo patients) will have at least 6 months active treatment by bumetanide.

The main burden of this study for the patient is related to the outpatient centre visits to follow up the safety of the diuretic effects, which requires physical examination [including blood pressure (SBP, DBP), heart rate, body weight, height], blood and urine tests, ECG and renal ultrasound, which are of low and known risks, as well as adverse event collection. Additional burden corresponds to cognitive test evaluations which are necessary for bumetanide efficacy assessment.

The Sponsor notes that these clinical studies will be carried out in a vulnerable population and has implemented several measures in order to minimize any potential burden:

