10.2.1.2. Treatment groups

For the 6-months double-blind period, treatment groups will be defined as:

- Bumetanide group
- Placebo group

It will correspond to allocated treatment by IRS except for safety analyses for which treatment received at W0 will be considered.

For the open-label active treatment period, treatment groups will be defined as:

- Bumetanide group : patients with Bumetanide 0.5 mg BID received at W0
- Placebo / Bumetanide group: patients with placebo received at W0 and treated by Bumetanide 0.5 mg BID in the open label period.

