10.2.2.4.2. Primary efficacy endpoint

The primary efficacy endpoint is the CARS total raw score, expressed in term of change from baseline to 6 month.

Primary analysis: Bumetanide will be compared to placebo using a general linear model with baseline CARS and stratification factors as covariates.

Missing data handling: CARS values post treatment discontinuation due to adverse event or lack of efficacy will be imputed using a reference based multiple imputation with a jump-to-reference approach. This approach assumes treatment benefit in patients who discontinue the Bumetanide arm disappears immediately upon discontinuation. Treatment effect estimation will take into account the situations when a patient can no longer tolerate or benefit from the treatment (occurrence of AE, lack of efficacy). CARS values post treatment discontinuation due to others reasons will be imputed using a multiple imputation approach assuming these patients could have theoretically continued to be treated without being put at undue risk.

Sensitivity analysis: sensitivity analyses detailed in the SAP to assess robustness to the method for handling missing data will be performed including a mixed model for repeated measurement.

Supplementary analysis:

The primary analysis will be repeated for the CARS total score expressed in term of change from baseline to 3 month.

The CARS total score and subscores will be summarized by treatment group at each planned visit for each period (double-blind treatment period and open-label active treatment period) using descriptive statistics.

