10.2.2.6. Safety analysis

10.2.2.6.1. Adverse events

Double-blind treatment period:

Number of events, number and percentage of patients reporting at least one event, presented by primary system organ class, and preferred term will be provided for serious adverse events and emergent adverse events under treatment during the double-blind treatment period in the Safety Set.

Emergent adverse events will be described according to the seriousness, the intensity, the relationship, the action taken regarding the IMP, the requirement of added therapy, and the outcome.

Of note, the seriousness and the relationship to the IMP of the adverse event correspond to the investigator opinion or, in case of events upgraded by the sponsor for seriousness or for causality in case of SAE, to the sponsor opinion.

Open-label active treatment period:

The same analysis will be performed for adverse events occurred or worsened during the open-label active treatment period in the Safety Set.

Post-treatment period:

All adverse events reported after the last study drug intake will be listed.

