2.2. Treatment arms

For the 26-week double-blind period, treatment arms will be defined as:

- S95008 arm.
- Placebo arm.

For the open-label period, treatment group will be defined as:

- Placebo/ S95008 arm: patients assigned to placebo group at W000 and treated by bumetanide 0.5 mg BID in the open-label period.

For the combined period (double-blind+open label periods), treatment group will be defined as:

- S95008 / S95008 arm: patients assigned to bumetanide 0.5 mg BID group at W000 and treated by bumetanide 0.5 mg BID in the open-label period.

It will correspond to allocated treatment by IRS except for safety analyses for which treatment received at W000 will be considered.

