The 100 datasets imputed for the primary analysis and supplementary analysis at W012 (based on the changes from baseline in CARS2 total scores) will be used to derive, the CARS2 responders. Analysis step will be based on the logistic regression model described above and then the combination step will be applied.

Statistical elements: the following elements will be provided in a summary table:

- Estimate (standard error) of the odds ratio between treatment groups.
- Two-sided 95% CI of the estimate.

- Descriptive analysis:

The CARS2 total score and subscores will be summarized using descriptive statistics and graphs (expect for subscores):

- During the double-blind period: baseline, each planned post-baseline visit (W004, W012 and W026) as well as change from baseline to each planned post-baseline visit will be described in the RS by treatment groups (S95008 vs placebo).
- During the open-label period: OL baseline, each OL planned post-baseline visit (W038 and W052) as well as change from OL baseline to each OL planned post-baseline visit will be described in the RSO for the Placebo/S95008 arm.
- During the combined period: baseline, each planned post-baseline visit as well as change from baseline to each planned post-baseline visit will be described in the RSC for the S95008/S95008 arm.
- At the follow-up visit (WEND), the change from the last post-baseline visit under treatment during the open-label period to WEND will be described in the RSO by treatment groups (S95008/S95008 vs Placebo/S95008).

The proportions of CARS2 responders will also be summarized at each planned post-baseline visit for each period.

The proportions of CARS2 performed remotely at baseline, W012 and W026 will be described in the RS by treatment groups (S95008 vs placebo).

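### The SAP leaves the continuing bumetanide arm out of its open-label efficacy and safety summaries, so no table gives months 6–12 safety incidence, or change from W026, for S95008/S95008

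*SAP*

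**What the plan says.** **Protocol.** Section 2 describes an "open label treatment period of bumetanide 0.5mg BID in which long term safety will be evaluated". Section 10.2.1.2 lists two groups for it: "Bumetanide group : patients with Bumetanide 0.5 mg BID received at W0" and "Placebo / Bumetanide group: patients with placebo received at W0 and treated by Bumetanide 0.5 mg BID in the open label period". Section 10.2.2.4.2 states that "The CARS total score and subscores will be summarized by treatment group at each planned visit for each period", and names the open-label period as one of the periods. Sections 10.2.2.4.3 and 10.2.2.5 say the same for SRS, Vineland II, PedsQL, WHOQOL-Bref and EQ-5D-3L. For safety, 10.2.2.6.1 states: "The same analysis will be performed for adverse events occurred or worsened during the open-label active treatment period in the Safety Set". Laboratory values and vital signs are to be reported by treatment period.

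**SAP.** Section 2.2 gives a single open-label group: "Placebo/ S95008 arm: patients assigned to placebo group at W000 and treated by bumetanide 0.5 mg BID in the open-label period". Section 3.6 applies this to safety: "For the open-label period: in the SSO on the Placebo/S95008 arm". Section 3.4.2.3 applies it to CARS2: "change from OL baseline to each OL planned post-baseline visit will be described in the RSO for the Placebo/S95008 arm". The other scales in 3.4 and 3.5 follow the same pattern. S95008/S95008 is reported over the combined period, with baseline at W000 and safety periods #5 and #6 starting at the first double-blind intake.

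**The concern.** Within the main study, only children randomised to bumetanide have more than six months of exposure. A harm that first appears after month 6 can be seen only in them, between W026 and W052. The SAP folds those weeks into a 12-month total, so the incidence tables do not answer the question for which the open-label period was set up.

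There is a smaller efficacy side. The switchers' W026–W052 change is a before-after figure in developing children whose families know they are now on active drug. The continuing arm over the same weeks is the one concurrent reference. It is a useful one, because Protocol 4.3 keeps investigators, raters and families unaware of the original assignment until the W000–W052 database lock. The SAP does not tabulate that arm's change from W026.

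**Working it through.** The plan states no figure on this point. The check sets the sections side by side and adds two illustrations on assumed inputs. The sample size (170 evaluable, 200 included) is unaffected.

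**1. Sections side by side, open-label period**

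| Output | Protocol | SAP, open-label | SAP, S95008/S95008 |
|---|---|---|---|
| Groups | both (10.2.1.2) | Placebo/S95008 (2.2) | combined period only (2.2) |
| CARS2, SRS-2, VABS II, PedsQL, WHOQOL-Bref, EQ-5D-3L | by group, each visit, each period (10.2.2.4, 10.2.2.5) | Placebo/S95008, change from W026 | change from W000 |
| CGI-I | rated against W026 at W038 and W052, no limit to one arm (7.2) | against W026, Placebo/S95008 (3.4.3.2) | against W000 only |
| Adverse events | Safety Set (10.2.2.6.1) | Placebo/S95008, #3 and #4 | #5 and #6 |
| Laboratory abnormalities | by period (10.2.2.6.2) | Placebo/S95008, #4 | #6 |
| C-SSRS-C | secondary safety endpoint (4.1) | Placebo/S95008, #4 | #6 |

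**2. Can the 12-month incidence stand in?** Let p1 be the risk of at least one event in months 0–6, and p2 the risk in months 6–12 among children without an earlier event. Then the 12-month incidence is 1 − (1 − p1)(1 − p2). With assumed risks:

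- 30% then 2%: 1 − 0.70 × 0.98 = 31.4%
- 17.2% then 17.2%: 1 − 0.828 × 0.828 = 31.4%
- 2% then 30%: 1 − 0.98 × 0.70 = 31.4%

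Falling, constant and rising risk give the same table entry. The annual rate in SAP 3.1.1 divides patients with an event by total patient-years, so it also averages the two halves.

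**3. Can months 6–12 be found by subtraction?** No. The double-blind table uses the SS. The combined table uses the SSC, which needs an open-label dose and a gap of under 30 days between periods (SAP 2.1), so the populations differ. Even in one population, the difference would count only children whose first event came after month 6; a child with events in both halves is counted once. S95008 children with a gap over 30 days enter neither the open-label nor the combined safety tables and are only listed (SAP 3.6).

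**4. Can the change from W026 be rebuilt?** Its mean can be approximated by subtracting visit means. Its spread cannot. With equal visit standard deviations s (assumed) and within-patient correlation ρ, the SD of change is s√(2(1 − ρ)): 1.18s at ρ = 0.3 and 0.45s at ρ = 0.9.

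**5. What the SAP does show of months 6–12 in S95008/S95008**

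- Combined-period values at W038 and W052 for most scales, where scheduled (3.4).
- Vital signs and ECG by visit (3.6.4).
- Open-label disposition by randomised group (3.2, 3.2.1).
- Both arms side by side at WEND for CARS2 and CGI-I (3.4.2.3, 3.4.3.2).
- Treatment-emergent adverse events by weeks to onset from the start of period #6 (3.6.1).

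None of these is an incidence for months 6–12 or a change from W026 to W038 or W052.

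**The case against.** The SAP structure has a coherent logic. Each arm is followed from its first bumetanide dose against a pre-drug baseline: W000 for the continuing arm and W026 for the switchers. The version history records that analysis sets and periods were added at version 3.0, so the layout looks deliberate. This supports the combined period as an addition. It gives no reason for removing a group that the protocol defines.

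Several stronger readings are tempting and are not supported:

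- **That months 6–12 in the continuing arm are never shown.** The outputs in step 5 above show parts of them. SAP 3.3.1 and 3.3.2 also describe open-label exposure and concomitant treatment in the SSO without naming an arm.
- **That late hypokalaemia would be hidden.** Potassium below 3.5 mEq/L is an adverse event of special interest with immediate notification on the adverse event page (Protocol 8.6, 8.7, 8.9.2.5), so its onset week can largely be located. The laboratory gap is mainly abnormalities not reported as adverse events. C-SSRS-C positives are also listed by patient (SAP 3.6.2).
- **That Protocol 10.2.2.6 requires open-label safety by group.** It refers to the Safety Set and to treatment periods. The group-wise wording is in the protocol summary sheet, and the two groups are in 10.2.1.2.
- **That the switchers' change will be claimed as a drug effect.** The main analysis is the double-blind period. Open-label efficacy is descriptive, and SAP 3.4.1 allows no p-value outside the primary analysis.

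One technical objection stands. W026 is an on-drug baseline for the continuing arm. Under SAP 3.6.3, a child already abnormal at W026 would not count as emergent afterwards, so the two open-label columns would not be like-for-like.

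**Conclusion.** The protocol and SAP differ, and the difference matters for the stated purpose of the open-label period. No planned table gives adverse event, laboratory-abnormality or C-SSRS-C incidence for months 6–12 alone in continuously treated children. No planned table sets a matching change from W026 in that arm beside the switchers' change. CGI-I against W026 is collected without limit to one arm but is not tabulated for S95008/S95008.

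The 31.4% example rests on assumed risks. It shows that the combined table cannot separate the two halves; it does not predict what the trial will find. The primary analysis, the sample size and the double-blind results are untouched. This is a correctable fault in descriptive reporting, with its main weight on safety. A reader should not infer that data are lost, or that the continuing arm is invisible after W026.

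**What to change.** In SAP 2.2, 3.4, 3.5 and 3.6, restore the protocol's two open-label groups. Show S95008/S95008 beside Placebo/S95008 in the open-label summaries: RSO and SSO, periods #3 and #4, baseline at W026 or W26B, and CGI-I against W026. Keep the combined period as an addition. Add a footnote that W026 is an on-drug baseline for S95008/S95008, so emergent laboratory counts are not like-for-like and the comparison is descriptive. If the sponsor prefers the present layout, the SAP should state the departure from Protocol 10.2.1.2 and the reason.

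The cost is SAP wording and a few more columns. RSO and SSO are defined without restriction by arm, periods #3 and #4 are defined by dates of intake, and the WEND summary already shows both arms in the RSO. No new data, visits or patients are needed.

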The emergent bumetanide safety profile observed in paediatric population with ASD was mainly related to bumetanide diuretic effect (enuresis, pollakiuria, polyuria, electrolyte disturbances and dehydration) and was dose-related. It did not differ from that of bumetanide tablets. Hypokalaemia is an identified risk and therefore blood potassium level will be regularly monitored during the phase III bumetanide paediatric program (blood potassium sampling schedule validated with the EMA). It has to be highlighted that all hypokalaemia reported during the phase II NeuroClin02 dose-range study were asymptomatic (and without any cardiac impact), and thus it is crucial to perform all planned samplings. Lastly, the most favourable tolerability profile was observed with bumetanide 0.5 mg twice a day corresponding to the dose that will be given during the 2 phase III studies.

Considering the targeted population of patients, a Data Monitoring Committee (DMC) will be set up and will be responsible for periodic review of patient's safety data throughout the study. Details on the role and organisation of the DMC will be provided in a separate charter. The study will be carried out in compliance with the protocol, GCP, the ethical principles that have their origin in the Declaration of Helsinki and the applicable regulatory requirements.

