- 1ml of bumetanide oral solution in the afternoon, 3 hours before going to bed at the latest.

Patients randomised in the placebo arm: from W000 to W026 visits will take placebo solution twice a day i.e.:

- 1ml of placebo oral solution in the morning at wake-up,
- 1ml of placebo oral solution in the in the afternoon, 3 hours before going to bed at the latest.

- **During the open label treatment period of 6 months:** from W026 to W052 visits

All patients will be treated by bumetanide.

➤ For patients with a weight $<$ 25 kg:

From W026 to W052 visits, patients will take 0.02 mg/kg of bumetanide twice a day:

- the volume of bumetanide oral solution (mL) = 0.04 x body weight (kg) in the morning at wake-up,
- the volume of bumetanide oral solution (mL) = 0.04 x body weight (kg) in the afternoon, 3 hours before going to bed at the latest.

➤ For patients with a weight \geq 25kg:

From W026 to W052 visits, the patients will take 0.5 mg of bumetanide twice a day, in the morning at wake-up and in the in the afternoon 3 hours before going to bed at the latest i.e.:

- 1ml of bumetanide oral solution in the morning at wake-up,
- 1ml of bumetanide oral solution in the afternoon, 3 hours before going to bed at the latest.

- **During the Follow-up period,** the patients will not be treated with IMP.

Table (4.4.1) provides a description of the IMP(s).

Table (4.4.1) 1 – Description of the IMPs

	S95008	Placebo
Pharmaceutical form	Oral solution	Oral solution
Unit dosage	0.5 mg/mL 1 mL corresponds to 0.5 mg of bumetanide	0
Appearance, colour	Colourless to pale yellow solution	Colourless to pale yellow solution
Composition	Bumetanide 0.5 mg Sodium methyl parahydroxybenzoate Sodium propyl parahydroxybenzoate	Sodium methyl parahydroxybenzoate Sodium propyl parahydroxybenzoate

Table (4.4.1) 2 and Table (4.4.1) 3 provide a description of the packaging of the IMPs.

Table (4.4.1) 2 – Description of packaging of the double-blind IMP

Number of units of the pharmaceutical form per primary packaging	60mL of S95008 or placebo oral solution in an amber glass bottle with polypropylene / low density polyethylene child-resistant and tamper-evident cap
Number of primary packaging per secondary packaging	2 bottles of S95008 or placebo per box with 2 graduated pipettes of 1mL
Number of secondary packaging per participant and per treatment period	1 box given per visit with allocation by the IRS

Table (4.4.1) 3 – Description of packaging of the open IMP

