6. TREATMENT OF PARTICIPANTS

6.1. IMP administered

During the run in and the follow up periods patients will not receive IMP.

During the treatment period (from W000 to W052), the patient will take orally twice a day:

- **in the morning at wake-up**

- **in the afternoon, 3 hours before going to bed at night at the latest**

the following volume of the oral solution:

For patients with a weight < 25kg:

- The volume (mL) = 0.04 x body weight (kg) twice per day from inclusion to W052

For patients with a weight ≥ 25kg:

- 1 ml twice per day from inclusion to W052

The study treatment should be taken at least 15 minutes before any food intake.

The first study treatment intake will take place in the afternoon at the latest 3 hours before going to bed at night of the inclusion visit day.

The last IMP intake will take place in the morning of the day of the scheduled visit.

The description of the IMP is detailed in Section 4.4.1.

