3.6.1. Adverse events

Definition:

- **Emergent Adverse Events (EAE)** during the double-blind (*resp. open-label, combined*) period are defined as all adverse events which occur in the period #1 (*resp. #3, #5*) (as per table above), or which started strictly before period #1 (*resp. #3, #5*) but which worsen (in terms of intensity) or become serious according to the investigator opinion during period #1 (*resp. #3, #5*).
- **Treatment Emergent Adverse Events (TEAE)** during the double-blind (*resp. open-label, combined*) period are defined as all adverse events which occur in the period #2 (*resp. #4, #6*) (as per table above), or which started strictly before period #2 (*resp. #4, #6*) but which worsen (in terms of intensity) or become serious according to the investigator opinion during period #2 (*resp. #4, #6*).
- **AE starting during the run-in period** are defined as all adverse events which started strictly before period #1.

Analyses:

Number of events as well as number, percentage and annual incidence rate of patients reporting at least one event, presented by primary System Organ Class (SOC), and Preferred Term (PT), will be provided for:

- Serious EAE and deaths for period #1, #3 and #5.
- TEAE, TEAE leading to IMP withdrawal, TEAE requiring new treatment or increase of ongoing treatment, TEAE requiring surgical or medical procedure, TEAE related to IMP, serious TEAE, severe TEAE, non-serious TEAE for periods #2, #4 and #6.

TEAE will be described according to the seriousness, the intensity, the relationship with the IMP, the action taken regarding the IMP, the requirement of added therapy and the outcome.

Moreover, TEAE, TEAE related to IMP and serious TEAE will be presented according to their time to onset in weeks calculated from the start of the period #2 (*resp. #4 and #6*).

AE starting during the run-in period will be also described by SOC and PT in the SS.

All adverse events reported after the last Bumetanide intake + 2 days (excluded) will be listed. All COVID-19 infection reported during the study will be listed.

Number of events as well as number, percentage of patients reporting at least one event, presented by primary System Organ Class (SOC), and Preferred Term (PT), will be provided for all AE and all serious AE occurring after the first intake in the extension part in the patients included in the extension period.

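### The SAP does not say where an adverse event on the W26 day belongs if it starts after a placebo child's first bumetanide dose; read by date, it is left out of the open-label tables

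*SAP*

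**What the plan says.** **Windows (SAP 3.6, Table (3.6) 1).** The lead-in reads "The start and end date of these periods are summarized in the following table". The relevant boundaries are:

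- Period #1 (emergent, double-blind) ends at "End of double-blind period (including W26".
- Period #2 (treatment-emergent, double-blind) ends at "Min(Last intake in double-blind + 2 days, First intake in open-label". The table does not say whether that end day counts, although it marks the ends of #4 and #6 as included.
- Periods #3 and #4 (open-label) start at "First intake in open-label (W26 not included".

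**Use of the windows (SAP 3.6 and 3.6.1).** TEAEs in the double-blind period are "all adverse events which occur in the period #2", plus earlier events that worsen or become serious within it. The other periods work in the same way. Only serious emergent events and deaths are tabulated on #1, #3 and #5; the TEAE tables use #2, #4 and #6. Open-label safety is reported for the Placebo/S95008 arm only, and the combined windows #5 and #6 for the S95008/S95008 arm only.

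**Dosing around W26.** Protocol 6.2 dispenses the first open-label kit at W026. Protocol 6.1 says "The last IMP intake will take place in the morning of the day of the scheduled visit". For children under 25 kg, Protocol 4.4.1 says "From W026 to W052 visits, patients will take 0.02 mg/kg of bumetanide twice a day", and the heavier children are also dosed twice daily. SAP 3.1.2 allows the open-label baseline to be measured on the day of W26 (or W26B), before the first intake of that period.

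**The concern.** The W26 day can hold two exposures for a placebo child: a placebo dose in the morning and a first bumetanide dose in the afternoon. A window rule that works in whole days and assigns W26 to the double-blind side puts the hours after that first bumetanide dose on the wrong side of the boundary.

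The day matters because SAP 3.4.2.1 describes bumetanide as having a rapid onset, and Protocol section 2 says that the safety profile seen in children "was mainly related to bumetanide diuretic effect (enuresis, pollakiuria, polyuria, electrolyte disturbances and dehydration". Such effects could appear within hours of a first dose.

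The handling is also uneven. In the double-blind period, #1 and #2 start at the first intake, so first-dose-day events count. For children on bumetanide throughout, #6 runs across W26 without a break. Only children switching from placebo can lose their first-exposure day.

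At stake are the placebo column of the only randomised safety comparison and the open-label incidence in newly exposed children. On a date reading, the error could raise the first or lower the second; either would favour bumetanide.

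**Working it through.** The plan states no figure on this point, so the check is to place events in the windows.

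**Step 1: when is the first open-label dose?** Open-label supply is handed out at W026, the last double-blind dose is that morning, and dosing is twice daily. The next dose is then due that afternoon. SAP 3.1.2 is consistent with this, since it separates W26-day measurements from the open-label intake that follows. Protocol 8.2 also counts the 72-hour limit for the first open-label electrolyte check from W026. The afternoon dose is still an inference: an afternoon first intake is stated outright only for inclusion.

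**Step 2: place an AE in a placebo child.** Assumed times on the W26 day: last double-blind dose 08:00, first open-label dose 16:00. Read by date, the end of #2 is the earlier of W26 + 2 days and the W26 day, which is the W26 day.

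| AE onset | #1 | #2, end day counted | #2, end day not counted | #3 and #4 |
|---|---|---|---|---|
| W26, 12:00 (before dose) | yes | yes | no | no |
| W26, 17:00 (after dose) | yes | yes | no | no |
| W26, 22:00 (after dose) | yes | yes | no | no |
| W26 + 1 day, 09:00 | no | no | no | yes |

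Read by clock time, with W26 meaning only the visit assessments, the 12:00 event is in #2 and the 17:00 and 22:00 events are in #3 and #4, as they should be.

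**Step 3: what reaches a table on the date reading?**

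- A serious post-dose event appears in #1 under placebo.
- If the end day of #2 counts, any post-dose event is a placebo TEAE and is missing from #4.
- If it does not count, the event is in neither #2 nor #4. A non-serious event is then in none of the planned double-blind or open-label AE incidence tables. The same happens to an event before the dose on that day.
- Periods #5 and #6 do not recover it, because they report the other arm.

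**Step 4: illustration of size.** The documents give no first-day event rate. Assume 100 placebo children, of whom 85 start open-label (the plan's 15% withdrawal), and first-day AE rates of 5%, 10% and 20%.

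- Events: 85 × 0.05 = 4.25; 85 × 0.10 = 8.5; 85 × 0.20 = 17.
- Placebo TEAE incidence, if the end day of #2 counts: up to 4.25, 8.5 or 17 points higher (events / 100).
- Open-label TEAE incidence (N = 85): up to 5, 10 or 20 points lower.

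These are upper bounds. Incidence counts children with at least one event, so the full shift needs every affected child to have no other TEAE in the period concerned.

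**The case against.** The strongest reply is that W26 in this table is a visit label. The same column of period ends names W52 and follow-up, which are visits, and the operative start of #3 and #4 is the first open-label intake. The parenthesis may only keep W26 laboratory, ECG, vital-sign and suicidality assessments, made before that intake, out of the open-label data. SAP 3.1.2 shows that the authors had the order of events on that day in mind. On this reading, with onset times recorded, post-dose AEs fall in #3 and #4.

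This stands as a possible reading. But the table's lead-in speaks of dates, laboratory, vital-sign and ECG values are also allocated by date (SAP 3.6.3 and 3.6.4), and SAP 3.6.1 has no onset-time rule. The documents do not show whether AE onset time is collected. Two programmers could produce different tables from the same text.

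Other limits also stand. Events that later worsen or become serious re-enter #3 and #4. The first open-label sodium and potassium check, at 48 to 72 hours, falls in #4. Time to onset is reported in weeks, so one day hardly moves it. Children who start open-label after the W26 day are not affected through W26 itself.

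A reader might infer that these events fall in no window at all. They do not: #1 includes W26, and the gap is in the treatment-emergent windows only. A reader might also infer that the placebo rate is inflated in every case. For TEAEs that requires the end day of #2 to count; otherwise the event is dropped rather than moved.

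**Conclusion.** The boundary is unclear, and on the date reading that the table's own wording supports, it misplaces or drops first-exposure events in children switching from placebo. They leave the open-label tables. Serious ones count under placebo in #1. As TEAEs they are either placebo events or in no treatment-emergent window. These last two are alternatives, and the SAP does not choose between them.

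The conclusion rests on an inferred first open-label dose on the W26 day and on W26 meaning the date. If it means only the pre-dose assessments, there is no misassignment and what remains is an unstated convention.

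The effect is confined to AEs that start on one day and do not later worsen or become serious. Its size cannot be derived from the documents, and the documents do not support a claim of a large shift in AE rates: the percentage-point figures above are ceilings under assumed rates. The correction is still worth making before the AE tables are programmed, because it is cheap and it touches the randomised safety comparison.

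**What to change.** In SAP Table (3.6) 1, separate assessments from adverse events:

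- Keep the W26 pre-dose assessments (laboratory, ECG, vital signs, C-SSRS-C) in #1 and #2.
- For AEs, end #1 and #2 just before the first open-label intake, and start #3 and #4 at that intake with that day included.
- Assign an AE dated the same day as the first open-label intake to the open-label period unless onset before that intake is recorded.
- Apply the same rule at W26B, for children with a delayed open-label start.

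With the assumed times above, the 12:00 event then falls only in #1 and #2, and the 17:00 and 22:00 events only in #3 and #4. Nothing is lost or counted twice across the double-blind and open-label windows.

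The cost is one table footnote and one programming rule. The downside is that a few AEs from the morning of W26 with no recorded onset time would be counted as open-label.
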